### **Protocol deviations**

The number (%) of patients in the FAS with any protocol deviation will be tabulated by deviation category overall for the FAS. All protocol deviations will be listed.

### **Analysis sets**

The number (%) of patients in each analysis set (defined in [section 2.2](#)) will be summarized.

## **5.4 Treatments (study treatment, concomitant therapies, compliance)**

### **5.4.1 Study treatment/compliance**

Duration of exposure, actual cumulative dose, dose intensity (DI) and relative dose intensity (RDI) will be summarized separately for each component of study treatment (dabrafenib and trametinib). The duration of exposure will also be presented for the study treatment of dabrafenib and trametinib combination therapy. Duration of exposure will be categorized into time intervals; frequency counts and percentages will be presented for the number(%) of subjects in each interval. The number (%) of subjects who have dose reductions, escalations or interruptions, and the reasons, will be summarized by dabrafenib and trametinib.

Patient level listings of all doses administered on treatment along with dose change reasons will be produced.

The safety set will be used for all summaries and listings of study treatment.

## Duration of exposure to study treatment

Duration of exposure to study treatment is considered by taking into account the duration of exposure to dabrafenib and trametinib:

Duration of exposure to study treatment (*days*) = (last date of exposure to study treatment) – (date of first administration of study treatment) + 1.

The last date of exposure to study treatment is the latest of the last dates of exposure to dabrafenib or trametinib.

Summary of duration of exposure of study treatment in appropriate time units will include categorical summaries and continuous summaries (i.e. mean, standard deviation etc.).

## Duration of exposure to dabrafenib and trametinib

Duration of exposure to dabrafenib (days) = (last date of exposure to dabrafenib) – (date of first administration of dabrafenib) + 1.

Duration of exposure to trametinib (days) = (last date of exposure to trametinib) – (date of first administration of trametinib) + 1.

**Table 2-2 Definition of last date of exposure of study drug**

Scenario	Definition of last date of exposure of study drug	Example
Daily administration of the study drug	Date of last administration of a non - zero dose of the study drug.	Example: A patient had a permanent discontinuation of the study drug 06Jan2013 after being put on a temporary interruption since 01Jan2013. In this case the last date of exposure is- 31Dec2012.

## Cumulative dose

Cumulative dose of a study treatment is defined as the total dose given during the study treatment exposure and will be summarized for each of the study treatment components.

The **planned cumulative dose** for a study treatment component refers to the total planned dose as per the protocol up to the last date of study drug administration. The planned cumulative dose will not be summarized/listed. It will be used for relative dose intensity calculations.

The **actual cumulative dose** refers to the total actual dose administered, over the duration for which the subject is on the study treatment as documented in the Dose Administration eCRF.

For patients who did not take any drug the cumulative dose is by definition equal to zero.

For continuous dosing, the actual cumulative dose is the sum of the non-zero doses recorded over the dosing period and the planned cumulative dose is the planned starting dose summed over the same dosing period.

### Dose intensity and relative dose intensity

**Dose intensity** (DI) for patients with non-zero duration of exposure is defined as follows:

$DI \text{ (mg / day)} = \text{Actual Cumulative dose (mg)} / \text{Duration of exposure to study treatment (day)}$ .

For patients who did not take any drug the DI is by definition equal to zero.

**Planned dose intensity** (PDI) is defined as follows:

$PDI \text{ (mg / day)} = \text{Planned Cumulative dose (mg)} / \text{Duration of exposure (day)}$ .

**Relative dose intensity** (RDI) is defined as follows:

$RDI = DI \text{ (mg / day)} / PDI \text{ (mg / day)}$ .

DI and RDI will be summarized separately for each of the study treatment components, but using the duration of exposure of each of the components.

**Table 2-3 Examples of dabrafenib dose administration and exposure**

DAR record number	Start/End date	Dose prescribed (mg), frequency	Dose administered (mg) [ total daily]	Dose changes, dose interruption	Dose permanently discontinued	Reason
1	01Jan2016 /05Jan 2016	150mg BID	300	No	No	AE
2	6Jan2016/03 Feb 2016	150mg BID	200	Yes	No	
3	04Feb2016/ 25Feb2016	150mg BID	300	No	No	

Duration of exposure (days) = 25Feb2016 – 01Jan2016 + 1 = 56 days

Planned cumulative dose (for 56 days) = 300\*56 days = 16800 mg

Actual cumulative dose = 300\*5 + 200\*29 + 300\*22 = 13900 mg

Dose intensity = 13900 mg / 56 days = 248.21 mg/day

Planned dose intensity = 16800 mg / 56 days = 300 mg/day

Relative dose intensity = DI / PDI = (248.21 mg/day) / (300 mg/day) = 83%

**Table 2-4 Examples of trametinib dose administration and exposure**

DAR record number	Start/End date	Dose prescribed (mg), frequency	Dose administered (mg) [ total daily]	Dose changes, dose interruption	Dose permanently discontinued	Reason
1	01Jan2016 /10Jan 2016	2 QD	2	No	No	AE
2	11Jan2016/15 Jan 2016	2 QD	0	Yes	No	
3	16Jan2016/25 Feb2016	1 QD	1	No	No	

Duration of exposure = 25Feb2016 – 01Jan2016 + 1 = 56 days

Planned cumulative dose (for 56 days) = 2\*56 days = 112 mg

Actual cumulative dose = 2\*10 + 0\*5 + 1\*41 = 61 mg

Dose intensity = 61 mg / 56 days = 1.09 mg/day

Planned dose intensity = 112 mg / 56 days = 2 mg/day

Relative dose intensity = DI / PDI = (1.09 mg/day) / (2 mg/day) = 54%

### Dose reductions, interruptions or permanent discontinuation

The number of patients who have dose reductions, permanent discontinuations or interruptions, and the reasons, will be summarized separately for each of the study treatment components.

‘Dose interrupted’ and ‘Dose permanently discontinued’ fields from the Dosage Administration CRF pages (DAR) will be used to determine the dose reductions, dose interruptions, and permanent discontinuations, respectively.

The corresponding fields ‘Reason for dose change/dose interrupted’ and ‘Reason for permanent discontinuation’ will be used to summarize the reasons.

A dose change is either ‘change in prescribed dose level’ or ‘dosing error’ where actual dose administered/total daily dose is different from the prescribed dose.

For the purpose of summarizing interruptions and reasons, in case multiple entries for interruption that are entered on consecutive days with different reasons will be counted as separate interruptions. However, if the reason is the same in this mentioned multiple entries on consecutive days, then it will be counted as one interruption.

**Reduction** is defined as a dose change where the prescribed dose level is lower than the previous prescribed dose level or where the actual dose administered/total daily dose is lower than the calculated dose amount based on the prescribed dose. Therefore any dose change to correct a dosing error will not be considered a dose reduction. Only dose change is collected in the CRF, number of reductions will be derived programmatically based on the change and the direction of the change.

## 5.4.2 Prior, concomitant and post therapies

### Prior anti-cancer therapy

The number and percentage of patients who received any prior anti-neoplastic surgery will be summarized. For prior surgery, time since last surgery, procedure and residual disease of last therapy will be summarized.

Separate listings will be produced for prior anti-neoplastic surgery.

Anti-neoplastic medications will be coded using the WHO Drug Dictionary (WHO-DD); anti-neoplastic surgery will be coded using MedDRA. Details regarding MedDRA and WHO-DD version will be included in the footnote in the tables/listings.

The above analyses will be performed using the FAS.

### Post treatment anti-cancer therapy

Anti-neoplastic therapies since discontinuation of study treatment will be listed and summarized by ATC class, preferred term and by means of frequency counts and percentages using FAS. Note that biopsies will not be regarded as an anti-neoplastic surgery for the purpose of this analysis.

The number and percentage of patients who reported taking at least one anti-neoplastic therapy since discontinuation of study treatment by category (e.g immunotherapy, targeted therapy, chemotherapy, radiotherapy, etc.), the duration of treatment and the best response will be summarized.

### Concomitant medications

Concomitant therapy is defined as all interventions (therapeutic treatments and procedures) other than the study treatment administered to a patient coinciding with the study treatment period. Concomitant therapy include medications (other than study drugs) starting on or after the start date of study treatment or medications starting prior to the start date of study treatment and continuing after the start date of study treatment.

Concomitant medications will be coded using the World Health Organization (WHO) Drug Reference Listing (DRL) dictionary that employs the WHO Anatomical Therapeutic Chemical (ATC) classification system and summarized by lowest ATC class and preferred term using frequency counts and percentages. Surgical and medical procedures will be coded using MedDRA and summarized by SOC and preferred term. These summaries will include:

1. Medications starting on or after the start of study treatment but no later than 30 days after start of last dose of study treatment and
2. Medications starting prior to start of study treatment and continuing after the start of study treatment.

All concomitant therapies will be listed. Any concomitant therapies starting and ending prior to the start of study treatment or starting more than 30 days after the last date of study treatment will be flagged in the listing. The safety set will be used for all concomitant medication tables and listings.

## 5.5 Analysis of the primary objective

The primary objective of the study is to assess whether an adapted AE-management algorithm for pyrexia will reduce the incidence of grade 3/4 pyrexia, hospitalization due to pyrexia, or permanent treatment discontinuation due to pyrexia compared to historical control from COMBI-AD study.

### 5.5.1 Primary endpoint

The primary endpoint is defined as the composite rate of grade 3/4 pyrexia (single preferred term), hospitalizations due to pyrexia or permanent treatment discontinuation due to pyrexia up to 12 months of therapy among overall treated patients.

The rate of this composite primary endpoint is calculated as the total number of patients experiencing at least one of the three components of the composite endpoint (i.e., Grade 3/4 pyrexia, hospitalization due to pyrexia, or permanent treatment discontinuation due to pyrexia), divided by the total number of patients in the FAS. The composite endpoint is assessed over a treatment period of 12 months; that is, any patient who experiences at least one of the components of the composite endpoint anytime within 12 month on-treatment will be included in the numerator for the calculation of the composite rate.

### 5.5.2 Statistical hypothesis, model and method of analysis

The primary analysis will be based on the calculation of the observed pyrexia event rate up to 12 months of therapy (primary endpoint) using the FAS. The observed pyrexia event rate will be summarized using descriptive statistics (N, %) along with its two-sided exact 95% confidence interval (Clopper and Pearson 1934).

In the COMBI-AD study, 87 out of 435 subjects in the treatment arm (20%) developed either grade 3/4 pyrexia or hospitalization due to pyrexia or discontinued due to pyrexia. This rate of 20% will be used as the historical control rate for the assessment of pyrexia management algorithm in this study.

Evidence of treatment effect (improvement in pyrexia event rate using the AE-management algorithm) will be concluded, if the upper bound of the two-sided 95% confidence interval is less than 20%.

The exact 95% confidence intervals for various observed event rates at the primary analysis are shown in [Table 2-5](#). This table has been updated from the protocol for the new sample size = 556 subjects.

If 92 (16.5%) out of 556 subjects are observed with pyrexia event, then the upper bound of the 95% confidence interval will be less than 20%.

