12.4.2 Statistical model, hypothesis, and method of analysis

The primary analysis will be based on the calculation of the observed pyrexia event rate up to 12 months of therapy (primary endpoint) using the FAS. The observed pyrexia event rate will be summarized using descriptive statistics (N, %) along with its two-sided exact 95% confidence interval (Clopper and Pearson 1934).

In the COMBI-AD study, 87 out of 435 subjects in the treatment arm (20%) developed either grade 3/4 pyrexia or hospitalization due to pyrexia or discontinued due to pyrexia. This rate of 20% will be used as the historical control rate for the assessment of pyrexia management algorithm in this study.

Evidence of treatment effect (improvement in pyrexia event rate using the AE-management algorithm) will be concluded, if the upper bound of the two-sided 95% confidence interval is less than 20%.

The exact 95% confidence intervals for various observed event rates at the primary analysis are shown in [Table 12-1](#). If 100 (16.7%) out of 600 subjects are observed with pyrexia event, then the upper bound of the 95% confidence interval will be less than 20%.

Table 12-1 Exact 95% CI for different observed event rates at primary analysis

N	r	Pyrexia event rate (%)	95% exact CI (%)*
600	100	16.7	13.8 – 19.9
600	101	16.8	13.9 – 20.1
600	102	17.0	14.1 – 20.2
600	103	17.2	14.2 – 20.4
600	104	17.3	14.4 – 20.6
600	105	17.5	14.5 – 20.8

N: Total numbers of subjects;

r: Number of subjects with pyrexia events at primary analysis

* Clopper and Pearson (1934)

In addition, the probability that the pyrexia even rate is below the threshold of 20% will be calculated from the posterior distribution. For illustration, as shown in [Table 12-2](#), if 104 out of 600 subjects are observed with pyrexia events at primary analysis, then the posterior probability of observing an event rate of < 20% is 0.954 (probability \geq 0.95).

Table 12-2 Posterior probability for a positive effect at primary analysis

N	r	Pyrexia event rate (%)	Posterior* Pr (event rate<20% data)
600	100	16.7	0.983
600	101	16.8	0.977
600	102	17.0	0.971
600	103	17.2	0.963
600	104	17.3	0.954
600	105	17.5	0.943
600	110	18.3	0.854
600	115	19.2	0.703
600	120	20.0	0.508
600	125	20.8	0.313
600	130	21.7	0.161
600	135	22.5	0.068

N: Total numbers of subjects;

r: Number of subjects with pyrexia events at primary analysis

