12.7 Interim analyses

One IA for futility of the primary endpoint is planned for the study when approximately the first 200 subjects dosed have been followed for 6 months (either completed 6 months of treatment or discontinued treatment earlier.) At the time of this IA, the futility of a secondary efficacy endpoint RFS will also be assessed. This analysis will allow assessing the impact of the adapted pyrexia AE-management algorithm on both the pyrexia event rate and the RFS rate at 6 months. The DMC will review the IA results and make a recommendation using the scenarios provided below. Any decision to stop or continue the pyrexia management algorithm will be made based on all data available at the IA cut-off taking the futility analysis into account.

From the COMBI-AD study that used the approved pyrexia management algorithm, the pyrexia event rate (composite rate of grade 3/4 pyrexia, hospitalization due to pyrexia, or permanent treatment discontinuation due to pyrexia) at 12 month observed for dabrafenib + trametinib (N=435) was: 20% with 95% CI (16%, 24%). Under the new pyrexia treatment algorithm, an observed primary endpoint rate of at least 20% may indicate lack of improvement of the new algorithm. Assessment of futility for primary endpoint will be based on the calculated Bayesian predictive probabilities of the event that observed pyrexia event rate will be 20% or more in the FAS, if the study is continued beyond the interim (i.e. till the primary analysis).

The pyrexia event rate is assumed to be binary and the number of subjects with pyrexia events is assumed to follow a binomial distribution. Suppose the prior belief regarding the probability of event rate (π) is that it has a beta distribution with parameters a_0 and b_0 . If there are x events out of n subjects, then the posterior distribution for π is beta with parameters $a_1 = a_0 + x$ and $b_1 = b_0 + n - x$. Now let Y represent the number of subjects with pyrexia events from m future observations, then the (posterior) predictive distribution of Y conditional on the observed data at the interim (x events out of n subjects) is a beta-binomial distribution described by

$$p(Y = y|x, n) = \binom{m}{y} \frac{B(a_0+x+y, b_0+n-x+m-y)}{B(a_0+x, b_0+n-x)}$$

where $B(a, b)$ is the beta function.

A diffuse (highly non-informative) prior distribution of the composite rate with a skeptical expectation of 20%, namely Beta (0.25, 1) is assumed.

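### The success rule tests this trial's rate against a fixed 20%, but the objective is a reduction from COMBI-AD, and no planned interval for that difference carries the sampling error of 87/435

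*SAP*

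**What the plan says.** SAP 5.5 states the primary objective as a comparison: whether the algorithm lowers the incidence of the composite "compared to historical control from COMBI-AD study".

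SAP 5.5.2 gives the source of the comparator, "In the COMBI-AD study, 87 out of 435 subjects in the treatment arm (20%) developed either grade 3/4 pyrexia" or one of the other two components, and fixes it: "This rate of 20% will be used as the historical control rate for the assessment of pyrexia management algorithm in this study". Improvement is concluded on the rule that Protocol 12.4.2 also uses: "if the upper bound of the two-sided 95% confidence interval is less than 20"%. The interval is Clopper-Pearson and uses this trial's data only. SAP 5.5.2 illustrates the boundary: "If 92 (16.5%) out of 556 subjects are observed with pyrexia event", the upper limit stays below 20%. Protocol 12.4.2 gives the counterpart for the planned size: "If 100 (16.7%) out of 600 subjects are observed with pyrexia event".

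Protocol 12.7 prints the COMBI-AD rate as "20% with 95% CI (16%, 24"%), but only as background to the futility assessment. The posterior probability in SAP 5.5.2 also uses a fixed 20%. The supportive analyses (SAP 5.5.4) and the COVID-19 sensitivity analyses (SAP 7.1) neither compare the two samples nor vary the benchmark.

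SAP 7.2 does mention a cross-study comparison of pyrexia outcomes between COMBI-AD and this trial, to support a possible label change, and lists the composite rate among its tables (item 27). It names no interval or test, and SAP Section 2 (Addendum details) leaves the label-update analyses out of the final analysis.

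**The concern.** The confidence attached to the success rule belongs to the statement that this trial's rate is below 20%. The objective makes a different statement, that the rate is lower than under COMBI-AD management. For that statement, 20% is an estimate from 435 patients, fewer than the 556 in this trial, and its sampling error is left out.

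At stake is how a narrow success is read. A result just inside the boundary would be reported as an improvement on COMBI-AD, possibly in support of a label change, while the data for that comparison are still compatible with no difference.

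**Working it through.** **Inputs.** 87/435 (SAP 5.5.2; Protocol 4.1 and 12.4.2); N = 556 (SAP 5.5.2) and N = 600 (Protocol 12.4.2); the rule of an exact 95% upper limit below 20%; the COMBI-AD interval of 16% to 24% (Protocol 12.7).

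**1. Reproduce the plan's figures.** The Clopper-Pearson limits are beta quantiles, lower Beta(0.025; x, n-x+1) and upper Beta(0.975; x+1, n-x).

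- 92/556: 13.6% to 19.9% (upper 19.90%), as in SAP Table 2-5.
- 93/556: 13.7% to 20.1%, as in SAP Table 2-5. So 92 is the largest count that succeeds.
- 100/600: 13.8% to 19.9%, as in Protocol Table 12-1.
- 87/435: 16.3% to 24.1%, matching the stated 16% to 24%.
- Posterior probability of a rate below 20% at 92/556: 0.982, as in SAP Table 2-6.

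**2. Difference from COMBI-AD at the boundary, 92/556 against 87/435.** d = 16.55 - 20.00 = -3.45 points. The Wilson limits are 13.69 to 19.86 for 92/556 and 16.51 to 24.01 for 87/435. The Newcombe limits are:

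- lower: -3.45 - √[(16.55-13.69)² + (24.01-20.00)²] = -3.45 - 4.93 = -8.4
- upper: -3.45 + √[(19.86-16.55)² + (20.00-16.51)²] = -3.45 + 4.81 = +1.4

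Pooled z: the pooled rate is 179/991 = 0.1806, SE = √[0.1806 × 0.8194 × (1/556 + 1/435)] = 0.0246, z = -1.40, two-sided p = 0.16 (Fisher 0.18). For 100/600 the difference is -3.3 points (-8.2 to +1.4), p = 0.17.

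**3. Where the two approaches part.**

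| Events | Plan's rule | Difference from 87/435 (95% Newcombe) | p (pooled z) |
|---|---|---|---|
| 84/556 (15.1%) | success | -4.9 (-9.8 to -0.1) | 0.043 |
| 85/556 (15.3%) | success | -4.7 (-9.6 to +0.04) | 0.052 |
| 92/556 (16.5%) | success | -3.5 (-8.4 to +1.4) | 0.16 |
| 93/556 (16.7%) | no success | includes zero | – |

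The band is 85 to 92 events of 556. For N = 600 it is 92 to 100, with 92/600 right at the edge (p = 0.0501).

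**4. Chance of success if the algorithm changes nothing.** This is P(X ≤ 92) for X ~ Binomial(556, p). It is a one-sided error, to be set against 2.5%.

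| True unchanged rate | 17% | 18% | 19% | 20% | 21% | 22% |
|---|---|---|---|---|---|---|
| P(success) | 41% | 20% | 7.6% | 2.2% | 0.5% | 0.08% |

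Averaged over Beta(87.5, 348.5), the Jeffreys posterior from 87/435, it is 8.6% for N = 556 and 9.0% for N = 600. If equal true rates are assumed instead and the benchmark is treated as re-estimated from 435 patients each time, it is 8.6% to 8.9% (N = 556) for true rates of 16% to 24%.

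**The case against.** Testing a single arm against a fixed reference is the usual formulation, and this one is disclosed. Protocol 4.1 explains the single-arm choice and says that the 20% rate will serve as comparator; 87/435 stands beside the rule in both documents, and Protocol 12.7 prints the interval. A reader can work out the difference. All of this stands: the rule is a valid one-sample test and the tables checked here are correct.

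Three stronger readings are tempting and should be resisted.

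- A reader might infer that no comparison with COMBI-AD is planned at all. SAP 7.2 names one; what is missing is an interval or test for the difference.
- A reader might take the 20% or 41% error at true rates of 18% or 17% as the rule's false-positive rate. Those are one side of the benchmark's uncertainty. If the true rate is above 20%, the rule is conservative (0.5% at 21%). Only the averaged figure is balanced.
- A reader might conclude that any success would be unsupported as a reduction. The disagreement covers eight event counts; below them both approaches show a reduction, and above them the plan's own rule fails.

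It is also fair to object to making the two-sample interval a condition for using the objective's wording. At a true rate of 15%, the chance of being allowed that wording would fall from 86% (P(X ≤ 92)) to 56% (P(X ≤ 84)); at 16%, from 66% to 31%. That is a second, stricter hurdle, and the point does not require it.

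**Conclusion.** The point holds as a matter of reporting and interpretation. The success rule supports the statement that the rate is below a fixed 20%; the objective claims a reduction from COMBI-AD, and the plan offers no interval that carries both samples' error for that claim. The effect is confined to 85 to 92 events of 556 (92 to 100 of 600). Over the benchmark's uncertainty the one-sided chance of success with no true change is about 8.6% (9.0% for N = 600), against 2.2% at exactly 20%.

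The documents do not support calling the rule invalid or the success criterion wrong. The figures assume independent binomial samples and the same endpoint definition in both trials. They cover sampling error only, so differences in population or ascertainment would come on top. They ignore the interim futility look, which barely matters: at a true rate of 20%, stopping at 44 or more events of 200 moves the success probability only from 2.19% to 2.18%.

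**What to change.** Keep the upper limit below 20% as the sole success criterion. In SAP 5.5.4 add, as a supportive analysis, the difference in proportions against 87/435 with a two-sided 95% Newcombe interval, and report it beside the primary result. In SAP 5.5.2 add one sentence stating that the 95% confidence of the primary rule refers to a rate below the fixed 20% benchmark. Do not make the added interval a second formal condition on the wording of the objective.

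Timing needs care. The last entry in the SAP's document history is dated 20 July 2021, and the primary cut-off was planned for 26 September 2020. If the analysis is added after the primary data cut-off, label it as not prespecified.

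The cost is one extra line of output from figures already in the documents. The downside is that a success at 85 to 92 of 556 would be shown beside an interval that includes zero.
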